9. RESEARCH METHODS

9.1. Study design

A population-based, non-interventional cohort study will be performed to identify and assess birth and pregnancy outcomes from HZ/su exposed pregnancies among women ages 18-49 years with IC conditions. A comparison group of pregnancies among women with IC conditions who were not exposed to HZ/su during pregnancy will be included and will serve as a reference to account for the contribution of different IC conditions on the safety outcomes of interest. The study will be conducted using health data held by three Data Partners that participate in the FDA's Sentinel System (described in Section 9.4).

The study period for identification of exposed and unexposed pregnancies for the cohort study will be July 1, 2021 to June 30, 2026. MCMs and additional infant outcomes (preterm birth, SGA, LBW, NICU admission, neonatal death) will be assessed in pregnancies resulting in a live birth for which the mother is linked to an infant. Since infant outcomes are generally captured in the infant's health plan claims, the mother's and infant's claims will be linked (see Section 9.2.1). Infants born from these pregnancies (exposed and unexposed) will be followed for up to one year of age for assessment of MCMs, the primary outcome of interest. Pregnancy outcomes will be assessed in pregnancies resulting in a live birth, non-live birth (stillbirth, spontaneous abortion).

214420 (EPI-ZOSTER-039 VS US DB) Protocol Amendment 2 Final

MCMs identified from this study will be validated by board certified teratologists. The teratologists will review the medical charts of each potential case and be blinded to treatment. Only validated cases will be used for main descriptive or comparative analyses (see Section 9.3.2).

Prior to initiating a cohort study, a feasibility assessment will be conducted (see Section 9.6.1.1) to identify counts of exposed live birth pregnancies during the period July 1, 2021 to June 30, 2023. If the feasibility assessment determines that it is not possible to identify an adequate number of exposed live birth pregnancies (see Section 9.5) among women with IC conditions for a cohort study (i.e., $\geq 1/3$ overall target), a descriptive analysis will be conducted (Section 9.7.3). The descriptive analysis will include HZ/su exposed and unexposed pregnancies (live birth and non-live birth pregnancies) among women with IC conditions identified in the feasibility assessment and their infants.

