9.3.2.1.1. Major Congenital Malformations

An MCM (birth defect or structural defect) is defined as a defect, which has either cosmetic or functional significance to the child (e.g., cleft lip). A detailed list of all major congenital malformations observed in live births compiled from the National Birth Defects Prevention Study (NBDPS) and the European Surveillance of Congenital Anomalies is provided in Appendix G Major Congenital Anomalies [Boyd, 2011; CDC, 2020; Rasmussen, 2003]. Consistent with the NBDPS case definition criteria, potential cases that occur as part of a genetic syndrome or other syndrome of known etiology (Appendix D: Diagnosis Codes for Chromosomal or Genetic Anomalies), or those that occur secondary to other major malformations (e.g., holoprosencephaly or amniotic band sequence) will not be included in the calculation of prevalence of major congenital malformations. Data for infants will be collected from delivery to 1 year of age, health plan disenrollment, death, or end of dataset (whichever comes first). Relevant codes will also be identified in the mothers' claims data for the first 30 days after the infant's date of birth.

MCMs identified from this study will be reviewed by board certified teratologists to confirm the diagnosis. The teratologists will review the medical charts of each potential case and be blinded to treatment. Only validated cases will be used in the main analyses.

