In addition to access to health plan claims data, all DPs have experience in medical chart retrieval procedures. The expected timeline for chart retrieval is generally between 3 to 6 months, depending on the facility/provider's willingness to participate. Many factors affect retrieval, including the number of facilities/providers to which outreach must be conducted, the type of chart (inpatient vs. ambulatory and whether an electronic health record (EHR) is accessible), and how far back records are requested. We expect chart reviews to be conducted for approximately 5% of pregnancies based on validation studies [Andrade, 2013; Cheetham, 2020; Cooper, 2008; Hansen, 2016; He, 2020]. It is anticipated that approximately 70-85% of requested charts will be returned with enough information (i.e., complete chart) to determine the presence or absence of MCM. Typically, the completeness of medical chart retrieval depends on the type of chart, the facility/provider, how many charts requested, and the type of information.

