9.5. Study size

All pregnancies among women who meet the study inclusion/exclusion criteria will be included in this study.

As the IC conditions included are heterogeneous and the number of MCMs for the primary outcome is likely small, the prevalence of each MCMs among each IC condition under study is not available. For sample size calculation for the cohort study, we employed the prevalence of overall MCMs (3%) in the general population [Holmes, 1976; Leppig, 1987; Marden, 1964; Van Regemorter, 1984] which might have a lower prevalence than among women with IC conditions. Therefore, the sample size calculated is relatively conservative. Assuming a 1:3 ratio of HZ/su-exposed to unexposed, a type 1 error of 0.05, and a target risk ratio of 2.0 for the primary safety outcome of MCMs, 711 live birth infants (live birth pregnancies linked to infant records) from the HZ/su-exposed group and 2133 live birth infants from the unexposed group will allow us to achieve 90% power.

The Power Analysis and Sample Size software (NCCS Statistical Software) was used in the sample size calculation.

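### The 90% power in section 9.5 takes the full 3% malformation prevalence, although only chart-confirmed cases count and 15–30% of requested charts are expected to be unusable

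*Protocol*

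**What the plan says.** - **Case definition.** Potential MCMs found in claims go to blinded chart review. Section 9.1: "Only validated cases will be used for main descriptive or comparative analyses". Section 9.3.2.1.1: "Only validated cases will be used in the main analyses".
- **Chart yield.** Section 9.4 expects review for about 5% of pregnancies, and that "approximately 70-85% of requested charts will be returned with enough information" to settle whether an MCM is present.
- **Study size.** Section 9.5: "we employed the prevalence of overall MCMs (3%) in the general population". It assumes a 1:3 ratio, "a type 1 error of 0.05, and a target risk ratio of 2.0 for the primary safety outcome of MCMs", and concludes that 711 exposed and "2133 live birth infants from the unexposed group will allow us to achieve 90% power".
- **Margin claimed.** Because prevalence in immunocompromised women might be above the general-population figure, section 9.5 adds: "Therefore, the sample size calculated is relatively conservative".
- **Alternatives.** Section 9.2.1.3 gives 812 + 1624 for a 1:2 ratio and 1108 + 1108 for 1:1, with the same 3% prevalence and 90% power.

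**The concern.** The sample size is built on true malformations; the main analysis counts confirmed ones. By the protocol's own expectation, 15–30% of requested charts will not allow a decision, and a true case behind such a chart cannot become a validated case. The event rate that drives power is then below 3% in both groups, and nothing in section 9.5 allows for it.

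This is a safety study, so its likely use is to interpret the absence of a detected doubling of risk. A null result read against 90% power reassures more than one read against about 80%.

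**Working it through.** **Inputs.** Baseline p0 = 0.03, ratio 2.0, alpha 0.05 (taken as two-sided, which reproduces the stated size), power 0.90, and k = 3 unexposed per exposed, all from section 9.5. Usable-chart fraction f = 0.85 or 0.70 from section 9.4.

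**Formula** (two proportions, pooled variance, no continuity correction), with p̄ = (p1 + k·p0)/(1 + k):

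- A = 1.960·√[(1 + 1/k)·p̄(1 − p̄)]
- S = √[p1(1 − p1) + p0(1 − p0)/k]
- exposed n = [(A + 1.2816·S)/(p1 − p0)]²
- power = Φ{[√n·(p1 − p0) − A]/S}

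**Step 1: reproduce 711.** With an odds ratio of 2.0, p1 = 2(0.03)/(1 + 0.03) = 0.05825 and p̄ = 0.03706. Then A = 0.4276, 1.2816·S = 0.3256, and n = (0.7532/0.02825)² = 710.7, which rounds up to 711. The same calculation gives 812 for 1:2 and 1109 for 1:1, against 812 and 1108 stated. With the labelled risk ratio of 2.0 (6% vs 3%), n is 641 and 711 gives 92.5% power. The printed sizes therefore match an odds ratio of 2.0, so both bases are carried forward.

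**Step 2: apply the chart yield.** Multiply both risks by f. The confirmed baseline is 0.03 × 0.85 = 2.55% or 0.03 × 0.70 = 2.10%. Example, odds-ratio basis at f = 0.70: risks are 4.078% and 2.10%, A = 0.3598, S = 0.2144, and power = Φ[(26.665 × 0.01978 − 0.3598)/0.2144] = Φ(0.78) = 78.3%.

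Results at 711/2133:

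| Effect basis | Quantity | No loss | 85% usable | 70% usable |
|---|---|---|---|---|
| Odds ratio 2.0 | power | 90.0% | 85.1% | 78.3% |
| Odds ratio 2.0 | exposed n for 90% | 711 | 842 | 1030 |
| Risk ratio 2.0 | power | 92.5% | 88.2% | 81.9% |
| Risk ratio 2.0 | exposed n for 90% | 641 | 760 | 929 |

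Fisher's exact test at a risk ratio of 2.0 gives 92.1%, 87.3% and 80.2%. Expected confirmed cases at a risk ratio of 2.0 fall from about 43 exposed + 64 unexposed to 36 + 54 or 30 + 45.

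**Step 3: the alternatives in section 9.2.1.3.** Same formula with k = 2 and k = 1:

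| Size | Basis | Power, 85% usable | Power, 70% usable |
|---|---|---|---|
| 812/1624 | odds ratio | 85.0% | 77.8% |
| 812/1624 | risk ratio | 88.1% | 81.6% |
| 1108/1108 | odds ratio | 84.5% | 76.8% |
| 1108/1108 | risk ratio | 87.9% | 80.8% |

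**Step 4: what would offset the loss.** Power at 711/2133 returns to 90% if true unexposed prevalence is about 3.6% (85% usable) to 4.5% (70% usable) on the odds-ratio basis, or 3.2% to 3.9% on the risk-ratio basis.

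**Cross-check within section 9.4.** If 5% of pregnancies are reviewed and 70–85% of those reviews are usable, 3.5–4.25% of pregnancies can be adjudicated. The design at a risk ratio of 2.0 implies a cohort-wide MCM prevalence of (0.06 + 3 × 0.03)/4 = 3.75%. At 70% this exceeds everything that could be adjudicated, even if every reviewed chart were a true case.

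**The case against.** - **The stated calculation is not a miscalculation.** True: 711 and 812 reproduce exactly and 1108 to within one. The fault is an omitted allowance.
- **The gap can be small.** At 85% usable charts and a literal risk ratio of 2.0, power is 88.2%, which is close to 90%. That is only because 711 exceeds the 641 needed at that effect. On the basis that generated 711, the shortfall is 5 to 12 points.
- **711 is not a cap.** Section 9.5 includes all eligible pregnancies, so accrual could exceed it. The 90% claim is nevertheless attached to 711 and 2133.
- **A rate per chart is not a rate per case.** A potential case may have several charts, and the 70–85% also covers false positives. This stands: equating chart yield with the share of cases confirmed is an assumption.
- **Handling of infants without a usable chart belongs in the SAP.** Sections 9.7.2.3 and 9.7.4 send misclassification analyses there, and the protocol does not say whether such infants are non-cases or are excluded. That silence is no finding. Either way the same events are lost, so the power figures hold.
- **Higher prevalence in immunocompromised women may cover the loss.** It may, per step 4. The protocol gives no figure for it, so neither side can be shown.

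A reader might also infer that the exclusion of chromosomal or genetic anomalies and of teratogen exposure pushes prevalence further below 3%. The documents do not show what the 3% includes and give no size for this, so it is not relied on.

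**Conclusion.** At the protocol's own inputs the stated 90% power is not met once the validated-only rule and the expected chart yield are applied. Power at 711/2133 is about 78–85% on the odds-ratio basis that reproduces 711, or 82–88% at a literal risk ratio of 2.0. Holding 90% would take 842–1030 or 760–929 exposed, respectively.

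This assumes true unexposed prevalence of 3%, a usable-chart rate equal to the share of true cases confirmed, retrieval independent of exposure and of case status, and claims codes that flag every case.

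Two stronger readings are not supported. One is that the comparison is biased: under these assumptions both groups lose the same fraction of cases, so the risk ratio is roughly unbiased. What suffers is precision and, if unadjudicated infants are counted as non-cases, absolute prevalence, which would be 15–30% too low. The other is that calling the size conservative is false. That sentence rests on a separate, unquantified premise, and a true prevalence of roughly 3.2–4.5% would offset the loss. It is unsupported, not disproved.

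**What to change.** 1. **Section 9.5:** restate power at a confirmed unexposed prevalence of 2.10–2.55%, on one stated effect measure. If the odds ratio of 2.0 behind 711 is kept, print 78–85% and label it so; if a risk ratio of 2.0 is meant, print 82–88%. The two should not be mixed.
2. **Section 9.2.1.3:** apply the same correction to the 1:2 and 1:1 sizes.
3. **Section 9.5:** qualify or delete the sentence calling the size relatively conservative, because higher prevalence in immunocompromised women may or may not offset the chart loss.
4. **Sections 9.1 and 9.3.2.1.1:** keep blinded, validated cases as the main analysis. Any imputation of confirmation status for infants without a usable chart should be a sensitivity analysis only. With 5% of 2844, about 142 flagged infants, and 70–85% usable, only some 100–121 charts would inform it.

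The cost is a less favourable power statement and a short text change; no data collection changes. If the sponsor chose to raise the target to hold 90%, the feasibility threshold of 237 in section 9.6.1.1, which is one third of 711, would have to move with it.

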9.5. Study size

All pregnancies among women who meet the study inclusion/exclusion criteria will be included in this study.

As the IC conditions included are heterogeneous and the number of MCMs for the primary outcome is likely small, the prevalence of each MCMs among each IC condition under study is not available. For sample size calculation for the cohort study, we employed the prevalence of overall MCMs (3%) in the general population [Holmes, 1976; Leppig, 1987; Marden, 1964; Van Regemorter, 1984] which might have a lower prevalence than among women with IC conditions. Therefore, the sample size calculated is relatively conservative. Assuming a 1:3 ratio of HZ/su-exposed to unexposed, a type 1 error of 0.05, and a target risk ratio of 2.0 for the primary safety outcome of MCMs, 711 live birth infants (live birth pregnancies linked to infant records) from the HZ/su-exposed group and 2133 live birth infants from the unexposed group will allow us to achieve 90% power.

The Power Analysis and Sample Size software (NCCS Statistical Software) was used in the sample size calculation.

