9.2.1.3. Comparison (Unexposed) Group

Unexposed pregnancies among women with IC conditions who were not vaccinated with HZ/su (i.e., not receiving at least one dose of HZ/su during pregnancy) will be selected as a comparator with a 3:1 matching ratio to the pregnancies among women with IC conditions who were vaccinated with at least one dose of HZ/su (exposed pregnancies). This matching ratio of 1:3 was chosen because it is feasible, reduces bias and increases precision. Matching will be conducted separately for the eligible cohort of live birth pregnancies linked to an infant (Primary Objective and Secondary Objective 1 cohort) and among the cohort of all eligible live birth and non-live birth pregnancies (Secondary Objective 2 cohort).

We will monitor and evaluate the 1:3 matching plan during the feasibility assessment to see how the matching plan performs.

If the proposed matching plan performs poorly in practice (i.e., many unmatched HZ/su-exposed pregnancies would be excluded), we propose the following alternative matching plans:

- a. Exact match strategies:
 - Exactly match on DP, combined primary IC condition categories, maternal age (± 10 years), start date of the pregnancy period (± 120 days)
 - Exactly match on DP, combined primary IC condition categories, start date of the pregnancy period (± 120 days) and put age in the propensity score
- b. Propensity match strategies: Nearest neighbor matching with caliper width at 0.02, 0.03, 0.04, 0.05, 0.1 and 0.2 between propensities of the unexposed HZ/su and the HZ/su exposed

We will consider reducing the matching ratio of HZ/su-exposed to unexposed to 1:2 or 1:1 if the desired sample size cannot be achieved even with the relaxed matching plan. The corresponding sample size for 1:2 ratio will be 2436 (812 exposed and 1624 unexposed) and 2216 for 1:1 ratio (1108 exposed and 1108 unexposed) when maintaining the other assumptions (i.e., 90% power, 3% MCM prevalence, a type 1 error of 0.05 and a target risk ratio of 2.0).

[figure not shown]
The unexposed pregnancies must be pregnant/reached the week of gestational age of the exposed pregnancy (i.e., when exposure occurred) without an adverse event (i.e., spontaneous abortion or stillbirth).

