9.6.1.1. Feasibility Assessment

During the feasibility period, annual assessments will be conducted to summarize the counts of HZ/su-exposed and unexposed live birth pregnancies among women with IC conditions (18-49 YOA). The counts of exposure to at least one dose of HZ/su will be stratified by calendar year of delivery, maternal age at pregnancy start date (5-year age groups), and IC condition.

Counts of women of childbearing age (18-49 YOA) with IC conditions who are HZ/su-exposed and unexposed will similarly be determined.

If the number of HZ/su-exposed pregnancies (live birth pregnancies linked to an infant) identified during the feasibility assessment is equal to or above 1/3 of the number of HZ/su-exposed pregnancies needed for the cohort study (n = 711 for cohort study and n = 237 for feasibility assessment, respectively), the feasibility assessment outcome will be categorized as 'Yes'. This indicates the target number of exposed pregnancies linked with live births could probably be identified during the five-year cohort study identification period, although it is not guaranteed.

If the number of HZ/su pregnancies identified during the feasibility assessment is less than one third of the target number of exposed pregnancies needed for the cohort study (i.e., n > 237), the feasibility assessment outcome will be categorized as 'No'. Should this be the case, the descriptive analysis, rather than the cohort study, will be conducted.

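### The stated sample sizes (711, 812, 1108 exposed) do not follow from a risk ratio of 2.0; they match an odds ratio of 2.0, a conservative mislabelling that should be corrected in wording

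*Protocol*

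**What the plan says.** Protocol section 9.5 takes the background risk from outside the study population: "we employed the prevalence of overall MCMs (3%) in the general population". It plans three unexposed infants for each exposed one and sets the error rate at 0.05. The design effect and the exposed group size then appear together: "a target risk ratio of 2.0 for the primary safety outcome of MCMs, 711 live birth infants". With 2133 infants in the comparison group, the section concludes that these numbers "will allow us to achieve 90% power". The abstract repeats these sizes and the risk ratio.

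Section 9.2.1.3 gives fallback sizes in case the matching ratio has to be reduced, on what it says are the same assumptions: "812 exposed and 1624 unexposed) and 2216 for 1:1 ratio (1108 exposed and 1108 unexposed".

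Section 9.6.1.1 builds the decision between a cohort study and a descriptive analysis on one third of the exposed target: "n = 711 for cohort study and n = 237 for feasibility assessment, respectively".

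None of these places says whether the test is one- or two-sided, and none names an odds ratio.

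**The concern.** The protocol gives every input to a standard two-proportion calculation except sidedness, so its sizes can be checked. They do not come out. All three stated exposed group sizes are about 11% above what a risk ratio of 2.0 requires.

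The design effect is therefore misdescribed: a reader who relies on section 9.5 will believe that the study was sized for a doubling of risk, when it was sized for something slightly smaller. The 711 also feeds the feasibility cut-off. Below that cut-off the study becomes descriptive, with no statistical comparison of malformation risk. Sections 7 and 9.6.1 expect few exposed pregnancies, so the position of the cut-off is not a formality.

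**Working it through.** **Inputs.** Unexposed risk p0 = 0.03, risk ratio 2.0, alpha 0.05, power 0.90 and k = 3 unexposed per exposed, all from section 9.5. k = 2 and k = 1 come from section 9.2.1.3. Two-sided testing is an assumption. Hence z for alpha = 1.960 and z for power = 1.2816.

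**Formula.** Pooled-variance comparison of two proportions, without continuity correction:

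n(exposed) = [1.960·√((1 + 1/k)·p̄(1 − p̄)) + 1.2816·√(p1(1 − p1) + p0(1 − p0)/k)]² / (p1 − p0)², where p̄ = (p1 + k·p0)/(1 + k).

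**Step 1: the stated effect.** A risk ratio of 2.0 gives p1 = 0.06. At k = 3, p̄ = 0.0375, and

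n = (0.42997 + 0.32949)² / 0.03² = 640.9.

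**Step 2: an odds ratio of 2.0.** The unexposed odds are 0.03/0.97 = 0.03093. Doubled they are 0.06186, so p1 = 0.06186/1.06186 = 0.05825, and the risk ratio is 0.05825/0.03 = 1.94. At k = 3, p̄ = 0.03706, and

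n = (0.42755 + 0.32562)² / 0.02825² = 710.7 (using the unrounded difference 0.028252).

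**Step 3: all three ratios.**

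| Exposed : unexposed | Stated exposed | Risk ratio 2.0 | Odds ratio 2.0 | Stated ÷ risk-ratio size (rounded up) |
|---|---|---|---|---|
| 1:3 | 711 | 640.9 | 710.7 | 711/641 = 1.109 |
| 1:2 | 812 | 732.2 | 811.3 | 812/733 = 1.108 |
| 1:1 | 1108 | 1001.4 | 1108.4 | 1108/1002 = 1.106 |

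Rounded up, the sizes for a risk ratio of 2.0 are 641/1923, 733/1466 and 1002/1002. The odds-ratio reading reproduces 711 and 812 exactly and 1108 to within one.

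**Step 4: power at the stated sizes.** For a risk ratio of 2.0 the same method gives 92.5%, 92.6% and 92.6%. For an odds ratio of 2.0 it gives 90.0% at each ratio. Fisher's exact test under a risk ratio of 2.0 gives 92.1%, 92.3% and 91.8%.

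**Step 5: other methods with a risk ratio of 2.0** (exposed at 1:3, 1:2, 1:1; stated 711, 812, 1108):

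- continuity correction: 685, 782, 1068
- one-sided test: 530, 603, 816
- unpooled variance: 772, 828, 998
- arcsine: 650, 732, 976
- log risk ratio: 578, 696, 1050

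None gives the three stated figures.

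**Step 6: the cut-off.** 711/3 = 237, as stated. For the stated effect, 641/3 = 213.7, so 214.

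**Step 7: chart retrieval.** Section 9.3.2.1.1 admits only validated cases to the main analysis, and section 9.4 expects 70–85% of requested charts to be usable. As an illustration, assume that true cases without a usable chart are lost in equal proportion in both groups. Observed risks are then 2.55% and 5.10% at 85%, and 2.10% and 4.20% at 70%. The 1:3 formula needs about 759 and 929 exposed respectively; one third is 253 to 310. Power for a true risk ratio of 2.0 would be 82–88% at 711 exposed and 78–85% at 641.

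**The case against.** The strongest defence is that nothing is lost. The error adds power, so the claim of 90% still holds for a risk ratio of 2.0. The effect actually powered, 1.94, is about 3% smaller than the one named. Section 9.5 includes all eligible pregnancies, so 711 does not cap the cohort. No endpoint, test or estimate changes. This stands, and it makes the point a correction of the record and not a threat to the study. It does not make the statement right: section 9.5 calls its size conservative only because of the choice of background prevalence, and declares no margin from the effect measure.

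A second defence is that the odds ratio is inferred. That also stands. No section names one as the design effect, the software output is not shown, and 1108.4 would normally be rounded up to 1109. Agreement at three separate ratios still makes the explanation very probable, and the mismatch with the stated inputs does not depend on it, beyond the two-sided assumption.

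A reader might infer that a count of 214–236 would wrongly turn the study into a descriptive one. The documents do not support so much. The one-third rule is a rule of thumb, and section 9.6.1.1 itself says that passing it does not guarantee the target. The feasibility period is two of the five identification years. At constant accrual the on-track count would be 711 × 2/5 = 284, or 641 × 2/5 = 256, and a count of 214 would project to 214 × 5/2 = 535, short even of 641. Uptake may rise, but the documents do not show that it will.

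**Conclusion.** The sizes in the abstract, 9.2.1.3 and 9.5 do not follow from their stated inputs. They are 10.6–10.9% above the requirement for a risk ratio of 2.0 and fit an odds ratio of 2.0 (risk ratio about 1.94). This rests on a two-sided alpha of 0.05, the only sidedness that matches, and on 3% being the unexposed risk. The direction is conservative, and the operational effect is confined to feasibility counts from 214 to 236.

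It is tempting to conclude that the target and the cut-off are too high and should come down to 641 and 214. The documents do not support that step. Once incomplete chart retrieval is allowed for under the assumption shown, a risk ratio of 2.0 needs more than 711 exposed, not fewer. This should be fixed, but it is not critical.

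**What to change.** Keep 711/2133, 812/1624, 1108/1108 and the cut-off of 237. In the abstract, 9.2.1.3 and 9.5, restate the target effect as an odds ratio of 2.0 (risk ratio about 1.94 at a 3% baseline) with a two-sided alpha of 0.05, and note that power for a risk ratio of 2.0 at 711/2133 is about 92.5%. Before doing so, check the saved software output to confirm that an odds ratio was entered.

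If the sponsor prefers to keep a risk ratio of 2.0 as the target, recompute all three sizes and the cut-off once, with the expected 70–85% chart retrieval in the same calculation, and align 9.6.1.1 as well. Do not lower the target or the cut-off on the effect-measure correction alone.

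The first option costs a wording change in three places. The second costs a rerun of the software and a stated assumption about unretrieved charts.
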